22.3 Grading and Attribution of Adverse Events

22.3.1 Grading Criteria

Adverse events will be graded according to the criteria set forth in the National Cancer Institute's Common Terminology Criteria for Adverse Events Version 5.0 [November 27, 2017; <http://evs.nci.nih.gov/ftp1/CTCAE/About.html>] This document (referred to herein as the NCI-CTCAE manual) provides a common language to describe levels of severity, to analyze and interpret data, and to articulate the clinical significance of all adverse events. All adverse events whether or not listed in the NCI-CTCAE will be graded on a scale from 1 to 5 according to the following standards in the NCI-CTCAE manual (A semicolon indicates 'or' within the description of the grade):

- Grade 1 Mild; asymptomatic or mild symptoms; clinical or diagnostic observations only; intervention not indicated.
- Grade 2 Moderate; minimal, local or noninvasive intervention indicated; limiting age-appropriate instrumental ADL*.
- Grade 3 Severe or medically significant but not immediately life-threatening; hospitalization or prolongation of hospitalization indicated; disabling; limiting self-care ADL**.
- Grade 4 Life-threatening consequences; urgent intervention indicated.
- Grade 5 Death related to AE.

*Instrumental Activities of Daily Living (ADL) refer to preparing meals, shopping for groceries or clothes, using the telephone, managing money, etc.

**Self-care Activities of Daily Living (ADL) refer to bathing, dressing and undressing, feeding self, using the toilet, taking medications, and not bedridden.

Not all Grades are appropriate for all AEs; therefore, some AEs are listed with fewer than five options for Grade selection.

Anaphylaxis is a disorder characterized by an acute inflammatory reaction resulting from the release of histamine and histamine-like substances from mast cells, causing a hypersensitivity immune response. Clinically, it presents with breathing difficulty, dizziness, hypotension, cyanosis and loss of consciousness and may lead to death. Severity grading of anaphylaxis as per the NCI-CTCAE manual is as follows:

- Grade 1= not applicable
- Grade 2= not applicable
- Grade 3= Symptomatic bronchospasm, with or without urticaria; parenteral intervention indicated; allergy-related edema/angioedema; hypotension
- Grade 4= Life-threatening consequences; urgent intervention indicated
- Grade 5= Death

Severity grading of AEs of laboratory abnormalities will be assessed as per the NCI-CTCAE manual.

22.3.2 Definition of Attribution

The site investigator will initially determine the relationship of an adverse event. The relationship of an AE to study participation will be determined is RELATED or UNRELATED.

22.3.3 Reporting Timelines

Reporting Serious Adverse Events to the Independent Safety Monitor

The Principal Investigator will notify the ISM by email of any SAE within 24 hours of becoming aware of the event. The ISM may request further information if necessary and possibly request changes to the protocol or consent form as a consequence of the adverse event.

Notifying Institutional Review Board

The Principal Investigator will ensure the timely dissemination of SAE information, including SAEs requiring expedited review by the ISM and to the IRB in accordance with IRB regulations and guidelines. Serious adverse events that are unanticipated, related to study participation, and involving risk to participant or others will be reported to the IRB within 10 business days of event occurrence or of the PI becoming aware of the event per IRB guidelines.

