- Temporarily halt receipt of statin therapy for three to 7 days and receive a new set of safety labs (CPK; LFTs) if they experience a grade 2 elevation in CPK (>2.5 x ULN - 5 x ULN) or LFTs (>3.0 - 5.0 x ULN) and without alternative etiology. If afterwards the labs are graded 1 or within normal limits, the participant may restart the statin therapy. If the labs do not trend to grade 1, the drug will be halted and the participant will be followed for safety and not vaccination if prior to D1.
- Permanently halt receipt of statin therapy if they experience a grade 3 elevation in CPK (>5 x ULN - 10 x ULN) or LFTs (>5.0 - 20.0 x ULN) after starting ST.
- The same rules apply to diarrhea and myalgias and other symptoms related to statin.

18. Risk to Participants

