22.2.4 Serious Adverse Event (SAE) or Serious Suspected Adverse Reaction

An adverse event or suspected adverse reaction is considered "serious" if, in the view of the investigator, it results in any of the following outcomes:

- Death
- A life-threatening adverse event
- Inpatient hospitalization or prolongation of existing hospitalization
- A persistent or significant incapacity or substantial disruption of the ability to conduct normal life functions
- A congenital anomaly/birth defect

Important medical events that may not result in death, be life-threatening, or require hospitalization may be considered serious when, based upon appropriate medical judgment, they may jeopardize the participant and may require medical or surgical intervention to prevent one of the outcomes listed in this definition. Serious adverse events will be reported and recorded for the entire duration of the study.

An adverse event or suspected adverse reaction is considered “life-threatening” if, in the view of the investigator, its occurrence places the patient or participant at immediate risk of death. It does not include an adverse event or suspected adverse reaction that, had it occurred in a more severe form, might have caused death.

Any serious adverse event (for duration of study) will be recorded and reported within 24 hours to ISM.

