22.2.6 Independent Safety Monitoring

The ISM, is a physician with relevant expertise in clinical studies whose primary responsibility will be to provide independent safety monitoring in a timely fashion and to provide recommendations regarding the safe continuation of this study.

The ISM will evaluate safety data generated from study participants against the known safety profile of the study product or study procedure to assess for possible changes to the overall risk of the study.

The ISM will communicate with the Principal Investigator as needed. The study has provisions for a back-up ISM to ensure that independent safety monitoring happens at all times during the study.

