22.4 Stopping Rules

Study Stopping Rules:

Study procedures will be suspended pending expedited review of all pertinent data by the institutional review board and the ISM if Atorvastatin or QIV were recalled by the manufacturer.

Also, procedures will be suspended pending review of all pertinent data by the ISM after the occurrence of any of the following:

- 1 case of statin-induced necrotizing autoimmune myopathy
- 1 case of acute liver injury
- 2 cases of severe myalgia

Individual participant Stopping Rules:

Early study termination will occur in participants due to any of the following circumstances detailed in Section 16.

Conditions for continuation of treatment or early termination of treatment/Follow-up:

Please refer to Section 17.

Follow-up After Early Study Termination:

Participants who are prematurely terminated from the study due to an AE will be followed until resolution of the AE or until 28 days after a participant terminates from the study. Resolution of an AE is defined as the return to baseline status or as stabilization of the condition with the expectation that it will remain chronic.

After assessing terminated participants for safety under the provisions stated above, the subject will be seen in clinic, if necessary.

Participant Replacement

In the case of premature termination (Day 8 or earlier), extra participants may be recruited, at the discretion of the Principal Investigator, to maintain the target sample size.

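### One rhabdomyolysis does not suspend the study although two severe myalgias do, and a non-serious grade 3 CPK or LFT rise has no set time for notice to the safety monitor

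*Combined protocol and SAP*

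**What the plan says.** **Timed notice to the ISM.** Section 22.3.3: "The Principal Investigator will notify the ISM by email of any SAE within 24 hours of becoming aware of the event". Section 22.2.4 repeats the rule: "Any serious adverse event (for duration of study) will be recorded and reported within 24 hours to ISM". Both cover SAEs only. Seriousness is the investigator's call. An important medical event that meets none of the listed outcomes "may be considered serious when, based upon appropriate medical judgment" supports that.

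**General remit.** Section 22.2.6 gives the ISM the task "to provide independent safety monitoring in a timely fashion" and adds: "The ISM will evaluate safety data generated from study participants against the known safety profile of the study product or study procedure". Contact with the principal investigator is as needed, with no interval.

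**Participant-level rule.** Section 17 says: "Permanently halt receipt of statin therapy if they experience a grade 3 elevation in CPK", with the band given as above 5 and up to 10 times the upper limit of normal (ULN). The liver function test (LFT) band is above 5 and up to 20 times ULN. No notice to the ISM is attached.

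**Study-level triggers.** Apart from a product recall, Section 22.4 suspends procedures pending ISM review for one statin-induced necrotizing autoimmune myopathy, "1 case of acute liver injury" or "2 cases of severe myalgia". Rhabdomyolysis is not on the list. Section 18.1 names it among the rarer, more serious risks.

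**The concern.** The muscle triggers do not line up with severity. Two severe myalgias, neither of which need be an SAE, pause the study. One rhabdomyolysis does not, and no reason is given.

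The second gap is about time. Section 17 treats a grade 3 CPK or LFT value as grounds for permanent discontinuation. Unless someone judges it serious, or calls it acute liver injury, nothing fixes when the ISM learns of it.

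What is at stake is mainly the protection of people not yet dosed. Section 10 allows 24 months for recruitment, so others may still be due to start 80 mg when a signal appears.

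**Working it through.** The plan states no figure on this point, so the check is a reading of the rules against each other, followed by simple binomial arithmetic for scale.

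**Step 1. Every route to the ISM**

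- SAE (22.2.4, 22.3.3): notice within 24 hours. The ISM may ask for information or request changes. No automatic suspension.
- Study-level trigger (22.4): suspension pending ISM review, for the listed events only.
- Section 17 grade 3 stop: no ISM step.
- General remit (22.2.6): no schedule for data delivery or review.
- Section 22 monitoring table, row on adverse event documentation: only SAEs are named for ISM evaluation.
- Section 22.1: regular adverse event review by the research team, not the ISM.

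**Step 2. Cases run through those rules**

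| Event in one or more statin recipients | Timed ISM notice? | Study suspended? |
|---|---|---|
| One necrotizing autoimmune myopathy | If an SAE | Yes |
| Two severe myalgias, neither an SAE | No time stated, but review is forced | Yes |
| One rhabdomyolysis, judged an SAE | Yes, 24 hours | No |
| The same case with severe myalgia | Yes, 24 hours | No; it counts as one of the two needed |
| Grade 3 CPK, not an SAE, no severe myalgia | No | No |
| Grade 3 LFT, not an SAE, called acute liver injury | No time stated, but review is forced | Yes |
| Grade 3 LFT, not an SAE, not called acute liver injury | No | No |

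Section 22.4 sets no threshold for acute liver injury, so which of the last two rows applies is a matter of judgment. CPK has no corresponding laboratory trigger.

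**Step 3. When such a value would be seen**

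Statin starts between D-31 and D-29 and runs to about 4 weeks after vaccination (Sections 5.1 and 6.2). After dosing starts, Appendix A schedules clinical labs at D1 and D29. There is also a phone call 15 days after the start (6.3) and repeat labs after a grade 2 value (Section 17). A grade 3 value at D1 ends dosing with about 4 weeks left. One first seen at D29 arrives as dosing ends, so its remaining protective use is mostly for other participants.

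**Step 4. Size**

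With n exposed and rate p, the expected count is n × p and the chance of one or more is 1 − (1 − p)^n. Take n = 30 (planned statin arm) and the rates in Section 18.1:

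- Serious muscle injury, p = 0.001 (stated as below 0.1%): 1 − 0.999^30 = 0.0296, about 3%. If replacements brought exposure to 35 (assumed): 1 − 0.999^35 = 0.034.
- Serious hepatotoxicity, p = 0.0001 (stated as below 0.01%): 1 − 0.9999^30 = 0.003.
- Persistent transaminases above 3 times ULN, p = 0.007: expected 0.21; 1 − 0.993^30 = 0.19. Persistent rises above 5 times ULN should be rarer, but this rate does not bound a single transient value.

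The documents give no rate for grade 3 CPK. If grade 3 or higher CPK or LFT rises combined occurred in 0.5% to 2% of recipients (assumed):

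- p = 0.005: expected 30 × 0.005 = 0.15; 1 − 0.995^30 = 0.14.
- p = 0.02: expected 30 × 0.02 = 0.60; 1 − 0.98^30 = 0.45.

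**The case against.** The strongest reply is that most of this is already handled. The affected participant is protected, because Section 17 stops the drug. Liver injury has a one-case trigger. Severe muscle symptoms have a trigger. The ISM has a broad and timely remit, and an important medical event can be classed as serious. The general scale in 22.3.1 describes grade 4 as life-threatening, which points towards an SAE, although laboratory values follow the CTCAE manual and the link is not automatic. All of this stands, and it narrows the second gap mainly to a grade 3 CPK rise without severe myalgia that nobody judges serious.

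On the muscle triggers, the list can be defended: severe myalgia may never be an SAE and so needs its own trigger, whereas rhabdomyolysis would usually reach the ISM within 24 hours anyway. That is a fair reading. It is weakened by the necrotizing myopathy item, which is also likely to be an SAE and still has a one-case trigger. It also leaves the difference between telling the ISM and pausing the study.

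A reader might infer that the ISM is shut out of non-serious data, or that a rhabdomyolysis would go unreported. The documents support neither. The remit in 22.2.6 covers participants' safety data generally, and the SAE rule would normally catch rhabdomyolysis. A reader might also conclude that a single LFT value above 5 times ULN ought to suspend the study. That does not follow: it would let one asymptomatic result halt a small trial, and the existing liver trigger leaves room for clinical judgment.

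**Conclusion.** Both gaps are real on the text and both are modest. One rhabdomyolysis does not pause dosing of other healthy volunteers, while two severe myalgias do. A grade 3 or higher CPK rise not judged an SAE has no set time for ISM notice; for LFTs the same gap is narrower.

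Expected events are few. The chance of about 3% for serious muscle injury rests on a general statin figure with no dose stated and on 30 people exposed. It should not be read as a ceiling: the trial gives 80 mg, and Sections 16 and 22.4 allow replacements. In the other direction, the trial enrolls ages 18 to 50 and excludes renal impairment from the statin arm, which removes two of the risk factors named in 18.1. The 0.5% to 2% range for laboratory values is an assumption with no anchor in the documents.

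This is an oversight matter at the level of a suggestion to consider, held with medium confidence. It changes no sample size, endpoint or analysis.

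**What to change.** 1. In Section 22.4, add to the trigger list: *1 case of rhabdomyolysis*.
2. In Section 22.3.3, add: *The PI will notify the ISM within 24 hours of becoming aware of any grade 3 or higher CPK or LFT elevation after statin initiation, including results at D29 or later, and will state any alternative etiology.*

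No automatic pause for a CPK or LFT value is proposed; the ISM decides after notice.

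The cost is one list item and one sentence. The first brings a small chance of a pause (roughly 3% on the general statin figure), which would be warranted if it came. The second brings an occasional extra email, between 0.15 and 0.6 expected over the study under the assumed rates. Some will concern CPK rises unrelated to the drug, which is why the notice should state any other cause.

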22.4 Stopping Rules

Study Stopping Rules:

Study procedures will be suspended pending expedited review of all pertinent data by the institutional review board and the ISM if Atorvastatin or QIV were recalled by the manufacturer.

Also, procedures will be suspended pending review of all pertinent data by the ISM after the occurrence of any of the following:

- 1 case of statin-induced necrotizing autoimmune myopathy
- 1 case of acute liver injury
- 2 cases of severe myalgia

Individual participant Stopping Rules:

Early study termination will occur in participants due to any of the following circumstances detailed in Section 16.

Conditions for continuation of treatment or early termination of treatment/Follow-up:

Please refer to Section 17.

Follow-up After Early Study Termination:

Participants who are prematurely terminated from the study due to an AE will be followed until resolution of the AE or until 28 days after a participant terminates from the study. Resolution of an AE is defined as the return to baseline status or as stabilization of the condition with the expectation that it will remain chronic.

After assessing terminated participants for safety under the provisions stated above, the subject will be seen in clinic, if necessary.

Participant Replacement

In the case of premature termination (Day 8 or earlier), extra participants may be recruited, at the discretion of the Principal Investigator, to maintain the target sample size.

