4. Study Endpoints

Primary Endpoint:

Magnitude of antibody responses to QIV at 29 days after vaccination in each study group.

Secondary Endpoint:

Frequency and severity of adverse events until Day 29 and serious adverse events until D181 after vaccination in each study group.

Exploratory Endpoints:

1. Identification of innate immune signatures until 7 days after vaccination that predict the magnitude and durability of Ab response Days 29, 91 and 181 after vaccination in each study group.
2. Plasma cytokine response until 7 days after vaccination in each study group.

5. Study Intervention/Investigational Agent

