5.1 Description

Atorvastatin therapy

Atorvastatin is a lipid-lowering agent of the statin family that functions by blocking a rate-limiting enzyme, HMG-CoA reductase, in the lipid metabolism. This agent is commonly used for primary and secondary prevention of dyslipidemia. Participants will be asked to take Atorvastatin 80 mg daily at night, for 4 weeks prior to the vaccination and continue the statin therapy for 4 weeks after vaccination.

The 80mg dose of atorvastatin allows for evaluation of the immunologic effects of statin medication with a short duration of therapy prior to vaccination. Studies have shown that 80mg of atorvastatin for 1 month affects inflammatory responses while lower doses of statin for longer periods may not. The 80mg dose reduced inflammation related to including NF- κ B while other studies looking at lower doses of statin for 3 months did not find a difference in NF- κ B¹⁹. Observational studies have investigated the dose-response question for statin therapy and vaccine effect but they either had insufficient sample size for that question²⁰ or there was a trend toward lower vaccine efficacy with higher dose statin, though this was not statistically significant²¹.

Quadrivalent seasonal influenza vaccine

The FDA-approved quadrivalent seasonal influenza vaccine contains four distinct strains: two influenza A viruses and two influenza B viruses. The approved seasonal QIV will be purchased from the manufacturer to be given for each season of influenza.

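### The follow-up limit in Section 22.4 for participants terminated for an AE stops short of the D181 SAE window, and no text says that endpoint collection continues.

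*Combined protocol and SAP*

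**What the plan says.** Section 4 and Section 7 define the secondary endpoint as "Frequency and severity of adverse events until Day 29 and serious adverse events until D181 after vaccination in each study group". Section 22.2.4 adds: "Serious adverse events will be reported and recorded for the entire duration of the study".

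Section 22.4 sets a separate rule for "Participants who are prematurely terminated from the study due to an AE": they "will be followed until resolution of the AE or until 28 days after a participant terminates from the study". It does not say whether the earlier or the later of the two applies. It continues: "Resolution of an AE is defined as the return to baseline status or as stabilization of the condition", where stabilization covers a condition expected to become chronic.

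Two other sections decide who falls under that rule.

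- **Section 16** lists reasons for study termination. The list is open-ended and does not name an AE, but 16.1 covers a participant who has ceased to meet the entry criteria. Data gathered before termination are kept unless consent is withdrawn.
- **Section 17** deals with statin toxicity by continuing, pausing or stopping the drug. For grade 2 labs that do not improve, "the drug will be halted and the participant will be followed for safety and not vaccination if prior to D1". For grade 3, the instruction is: "Permanently halt receipt of statin therapy if they experience a grade 3 elevation in CPK". Neither rule says that study participation ends.

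Section 7 plans descriptive AE tables and has no rule for unequal follow-up.

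**The concern.** The endpoint runs on a calendar fixed by vaccination. The 22.4 rule runs on a clock that starts at termination and is tied to one event. A site that follows 22.4 literally can close a vaccinated participant months before D181 although that person never refused contact. SAE counts would then rest on different lengths of observation, and the tables would not show it.

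The arms are also not equally exposed to the rule. Only one arm takes a drug, "for 4 weeks prior to the vaccination and continue the statin therapy for 4 weeks after vaccination", and only that arm has CPK, AST and ALT limits among its exclusion criteria. With 30 participants per arm and purely descriptive tables, one SAE that is missed or found changes what the safety table shows.

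**Working it through.** The plan gives no calculation on this point, so there is no figure to reproduce. The check is day arithmetic, followed by a reading of who can be affected.

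**Inputs.** AE window to Day 29 and SAE window to D181 (Section 4); 28-day limit (Section 22.4); 30 participants per arm (protocol synopsis, Section 7).

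**1. The 28-day limit.** For termination on day t, the last day of follow-up is t + 28. The shortfall against D181 is 181 − (t + 28) = 153 − t.

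| Termination day | Last day | Days short of D29 | Days short of D181 |
|---|---|---|---|
| D1 | D29 | 0 | 152 |
| D8 | D36 | 0 | 145 |
| D29 | D57 | 0 | 124 |
| D91 | D119 | 0 | 62 |
| D153 | D181 | 0 | 0 |

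For any termination on D1 or later, t + 28 is at least 29, so this limit does not touch the AE window.

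**2. What the *or* does.**

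- If the earlier date applies, early resolution shortens follow-up further. Assume 7 days from termination to resolution (my assumption). Termination on D1, D8 or D15 then ends follow-up on D8, D15 or D22, which is 21, 14 or 7 days before Day 29.
- If the later date applies, the D181 shortfalls in the table are upper limits, because a slow-resolving event extends follow-up. Even then, what is followed is that event.

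**3. Termination before vaccination.** Termination on D-15 plus 28 days ends on D13 or D14, depending on whether a Day 0 is counted, so 15 to 16 days before Day 29. If no vaccine is given, the endpoint window, which is defined from vaccination, does not exist for that person.

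**4. Weight of one case.** A full SAE record runs 181 − 1 = 180 days, so an arm of 30 contributes 30 × 180 = 5,400 days. One termination between D1 and D29 under the 28-day limit removes 124/5,400 = 2.3% to 152/5,400 = 2.8% of that.

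**5. How many.** The documents give no termination rate. Section 18.1 gives side-effect rates, which can only set a scale:

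- Persistent transaminases above three times ULN, 0.7%: 30 × 0.007 = 0.21 expected cases; chance of at least one = 1 − 0.993^30 = 19%.
- Muscle symptoms of any severity, 3 to 8%: 0.9 to 2.4 expected cases; chance of at least one 60 to 92%. Most of these would not end participation.

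**6. A route specific to the statin arm.** Section 11 excludes statin-arm participants with CPK, AST or ALT at or above 1.5 times ULN. Section 6.4 reviews eligibility again on D1, and Appendix A places statin safety labs on D1 and D29. Section 16.1 allows termination for lost eligibility. Section 17 keeps a participant on drug with CPK up to 2.5 times ULN or LFTs up to 3.0 times ULN. A value of 2 times ULN on D1 is therefore a reason to continue under one section and a possible reason to terminate under another. Anyone terminated by this route before the injection falls under step 3; anyone terminated after it falls under step 1.

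**The case against.** The strongest reply is that 22.4 reaches few people. It treats study termination (referred to Section 16) and stopping the drug (referred to Section 17) separately, and Section 17 sends statin toxicity down the second path, in one case with safety follow-up that has no end date. A reader might infer that the participants most affected by the statin are the ones cut off. The documents do not support that: on the text, their drug stops while they stay in the study. This part of the objection stands. It does not remove the point, because 22.4 itself provides for AE terminations, Section 16 is open-ended, and 16.1 offers the route described above.

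A reader might also infer that the Day 29 AE window is routinely lost. It is not: after vaccination the 28-day limit always reaches Day 29, and a loss needs the whichever-is-first reading, which 22.4 does not state.

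It can further be said that 22.4 governs only the triggering event, and that Sections 22.2.4 and 22.2.7 record SAEs throughout the study. That is a fair reading, but those sections do not say whether the study is still running for someone already terminated. Pregnancy is the one withdrawal for which 22.2.7 spells out longer follow-up.

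Finally, the triggering AE is still counted, the rule covers both arms, and the analysis is descriptive. Appendix A also records AEs at the statin-initiation visit and the phone call, so before vaccination the statin arm may be observed for longer. All of this stands. A claim that the comparison is biased in a known direction, or by a known amount, would go beyond the documents.

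**Conclusion.** The point holds in limited form. For a participant terminated for an AE, the 22.4 limit and the D181 SAE window do not agree, no text carries collection on, and the analysis has no provision for unequal follow-up. When the 28-day limit decides, the shortfall is 124 to 152 days for termination between D1 and D29 and disappears only from D153 onward.

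Confidence is high in the conflict between the sections and low in its practical size. The number affected cannot be derived from the documents; zero to a few is a reasonable expectation, since the Section 18.1 rates are side-effect rates and not termination rates. That loss is more likely in the statin arm rests on two assumptions: that sites apply the lab exclusions again after the statin has started, and that they use 16.1 when a participant fails them. It is still worth correcting, because data not collected after a participant is closed out may not be recoverable.

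**What to change.** 1. Amend Section 22.4 to say that, unless the participant refuses further contact, AE collection to Day 29 and SAE collection to D181 continue after statin discontinuation or termination for an AE, by phone if visits have stopped. This is in addition to following the triggering event.
2. State in 22.4 whether the earlier or the later of the two dates applies, and that it governs only the triggering event.
3. Reconcile Sections 16, 17 and 22.4 on whether stopping the statin for an AE ends study participation, and on whether the statin-arm lab exclusions are applied again after the drug has started. Which clinical rule applies is for the investigators to decide.
4. In Section 7, report follow-up time by arm beside the AE and SAE tables.
5. Report participants terminated before vaccination separately, because the endpoint is defined after vaccination.

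The cost is a short amendment with IRB approval and the matching consent-form revision (Sections 25.1 and 25.2), plus a few extra phone contacts. No treatment rule needs to change for the data-collection part.
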